5.3 Statistical analysis

Reflecting the possible clustering in the data, the outcomes will be compared using multilevel models, with adjustment for minimisation variables and participant baseline values. Statistical significance will be at the 2.5% level with corresponding confidence intervals will be derived. All participants will remain in their allocated group for analysis (intention to treat). Comparisons (i) and (ii) will be based upon the respective direct randomised evidence only. For comparison (iii), a meta analysis will be used to combine the results from the direct comparison (using stratum A) and an indirect comparison (using strata B and C). A secondary analysis will investigate the impact of surgical expertise level (learning curve effects)¹⁷. All study analyses will be according to a statistical analysis plan that will be agreed in advance by the Trial Steering Committee. A single main analysis will be performed at the end of the trial when all follow up has been completed. An independent Data Monitoring Committee (DMC) will meet early in the trial to agree its terms of reference and other procedures and will review confidential interim analyses of accumulating data at least annually as directed.

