7.2.1 Lead consultant surgeon

Each collaborating centre will identify a lead consultant surgeon who will be the point of contact for that centre. The responsibility of this person will be to:

- establish the study locally (e.g. facilitate local research ethics committee approval, liaise with the local R&D manager and inform all relevant local staff about the study)
- take responsibility for the conduct of the research locally
- notify the study office in Oxford of any unexpected clinical events which might be related to study participation
- provide support and supervision for the local research nurse if applicable
- represent the centre at UKUFF collaborators meetings
- initiating recruitment of participants
- maintaining communication with the study office in Oxford regarding allocated surgical treatment, date of operation, discharge instructions and surgery withdrawal
-

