7.6 Data and Safety monitoring

7.6.1 UKUFF Data Monitoring Committee

The Data Monitoring Committee is independent of the study organisers. The chairman is [name], a Reader in Orthopaedic Surgery, along with [name] (Reader in Physiotherapy) and [name] (Senior Lecturer in Medical Statistics). During the period of recruitment to the study, interim analyses will be supplied, in the strictest confidence, to the data monitoring committee, together with any other analyses that the committee may request. This may include analyses of data from other comparable trials. In light of these interim analyses, the Data Monitoring Committee will advise the Steering Committee if, in its opinion, the trial has provided both:

- a) proof beyond reasonable doubt that for all or some types of participants one intervention is clearly indicated in terms of clinical and cost effectiveness
- b) evidence that might reasonably be expected to influence materially the care of the people with rotator cuff tears by clinicians who know the results of this and comparable trials.

The Steering Committee can then decide whether or not to modify intake to the trial. Unless this happens, the Steering Group, Management Group, consultant surgeons and study office staff (except those you supplied the confidential analyses) will remain ignorant of the interim results.

The frequency of the interim analyses will depend on the judgement of the Chairman of the committee, in consultation with the Steering Committee.

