11. PUBLICATION

The success of the trial depends entirely on the wholehearted collaboration of a large number of health care workers. For this reason, chief credit for the trial will be given, not to the committees or central organisers, but to all those who have wholeheartedly collaborated in the trial. The trials' publication policy is described in Appendix IX. The results of the trial will be reported first to trial collaborators. The main report will be drafted by the UKUFF Management Group, and the final version will be agreed by the Trial Steering Committee before submission for publication, on behalf of the UKUFF collaborators.

To safeguard the integrity of the main trial, reports of satellite studies will not be submitted for publication without prior agreement from the UKUFF Management Group.

We plan to maintain interest in the study by publication of UKUFF newsletters at three monthly intervals for collaborators and annually for participants. The newsletters will inform their audience of how the study and recruitment is progressing and any relevant interim results. UKUFF have deemed it important to communicate with the collaborators so that common problems may be addressed and protocol adherence may be monitored.

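### Section 11 plans newsletters carrying interim results to collaborators and participants, which contradicts the confidentiality of interim results in sections 7.6.1 and 5.3

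*Protocol*

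**What the plan says.** **Newsletters (Protocol, section 11).** The trial plans "newsletters at three monthly intervals for collaborators and annually for participants". On content: "The newsletters will inform their audience of how the study and recruitment is progressing and any relevant interim results". The section sets no limit to pooled data and does not refer to the DMC. It gives the purpose as keeping up interest, dealing with shared problems and monitoring adherence to the protocol.

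**Confidentiality (Protocol, section 7.6.1).** During recruitment, "interim analyses will be supplied, in the strictest confidence, to the data monitoring committee". The DMC advises the Steering Committee if two stated conditions are both met, and the Steering Committee then decides whether to modify intake. Otherwise the Steering Group and the "Management Group, consultant surgeons and study office staff (except those you supplied the confidential analyses) will remain ignorant of the interim results". The bracket evidently means the staff who supply the analyses.

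**Analysis (Protocol, section 5.3).** The DMC "will review confidential interim analyses of accumulating data at least annually as directed".

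**Who the collaborators are (Protocol, section 7.2.1).** One duty of the lead consultant surgeon is to "represent the centre at UKUFF collaborators meetings", so surgeons are among the newsletter's readers.

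**The concern.** The same people are promised interim results in one section and required not to know them in another. Those who would be expected to prepare a newsletter, the Management Group and study office staff, are also on the list of people kept ignorant. Apart from the staff who supply the analyses, they could not write what section 11 describes without breaching 7.6.1.

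This trial is exposed to the effects of early release for three reasons:

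- **Allocation is known.** Participants, surgeons and GPs are told it by letter (sections 3.4.1 and 3.4.2). The only blinded assessor described is the radiologist who reads the MRI scans (section 4.2).
- **The primary outcome is self-scored.** It is the OSS at 24 months (section 5.1), completed by the participant. Section 4.1 rightly says that this avoids interviewer and rater bias, but it gives no protection against a participant's own knowledge of results.
- **Treatment and recruitment can respond.** Rest then Exercise participants stay on the surgical waiting list and may decline surgery after the programme (section 3.4.2). Strata depend on each surgeon's willingness to randomise (section 2.2).

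Results by arm could therefore affect whom surgeons approach, cross-over between arms, and the scores themselves.

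**Working it through.** The protocol states no figure on this point, so the check is mainly a comparison of text, followed by a count of exposure.

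**1. The rules side by side**

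| Reader | Section 11 | Section 7.6.1 | Result |
|---|---|---|---|
| Consultant surgeons | Receive interim results every three months, as collaborators | Named as remaining ignorant | Direct contradiction |
| Management Group, study office staff | Expected to prepare the newsletters (an inference) | Named as remaining ignorant, except those who supply the analyses | Cannot follow both |
| Participants | Receive interim results every year | Not named | Conflict only with the confidentiality wording in 7.6.1 and 5.3 |

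**2. Number of issues before the main analysis.** The protocol gives no start date, so I assume that newsletters run from the opening of recruitment. Section 7.1 puts recruitment in months 4 to 30 and the end of 24-month follow-up at month 54.

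- Quarterly issues during recruitment: (30 − 4)/3 = 8.7, so about 8.
- Quarterly issues to the end of follow-up: (54 − 4)/3 = 16.7, so about 16.
- Annual issues to participants: (54 − 4)/12 = 4.2, so about 4.

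**3. Primary outcomes still to come.** Section 6.2 expects 16, 142, 320, 507 and 690 recruits by months 6, 12, 18, 24 and 30. Ignoring attrition, outcomes pending at month *m* = 690 − recruits by month (*m* − 24).

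- Month 30: 690 − 16 = 674 (98%).
- Month 42: 690 − 320 = 370 (54%).
- Month 48: 690 − 507 = 183 (27%).

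**4. Is there anything to release while most primary outcomes are pending?** Yes, from earlier time points. The 12-month OSS is a secondary outcome (section 5.1). At month 30 it could be available for those recruited by month 18, which is up to 320 of 690 (46%). At month 24 it could be available for up to 142, with 690 − 507 = 183 participants still to be recruited and no 24-month score yet due.

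These counts describe exposure. They do not estimate bias.

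**The case against.** The strongest reply is that section 11 is loose drafting and not a decision to unblind. It speaks of a plan, says nothing of results by arm, and has an operational purpose. Interim results could mean pooled information, or results released after the 7.6.1 process. Most of the staff concerned would hold no comparative results to print. Appendix IX (publication policy) and Appendix XI (DMC terms of reference) are not in the text at hand and may restrict content.

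Much of this is fair. A reader might infer that the trial has decided to publish comparative results as it goes along, and the text does not show that. But section 11 states no limit, lists interim results in addition to progress and recruitment, and uses the same term that 7.6.1 uses for what must be withheld. An appendix could clarify the intention, but the main text would still contradict itself.

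Three other stronger readings are tempting and are not supported:

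- **That section 5.3 forbids interim results altogether.** It says "A single main analysis will be performed at the end of the trial when all follow up has been completed", but it also provides for interim analyses by the DMC, and the two are compatible. The relevant word there is that those analyses are confidential.
- **That 7.6.1 expressly bars release to participants.** They are not on its list.
- **That the false-positive rate rises by a stated amount.** Such a figure needs an assumed shift in OSS, for which the documents give no basis. Applying it to all 190 per arm would also be wrong, because scores already returned cannot move.

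Nor is it right that nothing could be done afterwards. Missing questionnaires and cross-over can be partly examined in sensitivity analyses. Bias in self-scoring cannot be removed in that way.

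**Conclusion.** The contradiction stands. It is explicit for consultant surgeons, the Management Group and study office staff, and implied by the confidentiality wording for participants. If section 11 were followed as written and results by arm were included, the trial would breach its own safeguard while most primary outcomes were pending (98% at month 30, 54% at month 42).

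The conclusion rests on reading collaborators to include surgeons, which section 7.2.1 supports, and on inferring from the allocation letters and the nature of the interventions that participants and surgeons are unblinded. The exposure counts also assume that recruitment meets the milestones in section 6.2. The bias is a plausible risk whose size cannot be computed from the documents. The point is more than clerical, because results once released cannot be recalled.

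**What to change.** In section 11, replace the last five words of the sentence on newsletter content with: *and non-comparative (pooled) information only; no outcome or complication results by allocated group are released before the main analysis except through the route in 7.6.1.*

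This still allows recruitment figures, pooled baseline data and overall follow-up rates. Pooled should mean across strata as well as arms: under section 2.2 the only surgical arm is arthroscopic in Stratum B and open in Stratum C, so surgical results shown by stratum would in effect be results by technique.

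The cost is one sentence in the protocol and a content check before each issue. The only downside is less newsworthy newsletters.
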